ACCORDS

ADULT AND CHILD CENTER FOR OUTCOMES
RESEARCH AND DELIVERY SCIENCE

UNIVERSITY OF COLORADO
CHILDREN'S HOSPITAL COLORADO

Supporting the Implementation of a State Policy on Screening for Adverse Childhood
Experiences (ACEs) in Federally Qualified Health Centers (FQHC).

Statistical Analysis Plan

NCT: 04916587

Date: 7.20.2024

Statistical Analysis Plan

Title of Study: Supporting the Implementation of a State Policy on Screening for Adverse Childhood Experiences (ACEs) in Federally Qualified Health Centers (FQHC)

NIMH Study ID Number: R21MH123835

Clinical Trial Number: NCT04916587

Sponsor: Study funded by the National Institute of Mental Health.

Principal Investigator: [name] [name].

Summary and research objective(s):

Screenings for Adverse Childhood Experiences (ACEs) promote early identification of toxic stress and potential trauma, allowing for intervention and possible amelioration of detrimental effects of the ACEs. The state of California enacted a 2020 fee-for-service healthcare policy, ACEs Aware, reimbursing clinics for annual ACEs screenings during well-child visits, but did not provide guidance on screening implementation. This study aims to test the effectiveness and acceptability of a multifaceted implementation strategy for implementing ACEs screenings, in partnership with a Federally Qualified Health Center (FQHC) system in California that adopted the ACEs Aware policy in August of 2020.

The proposed strategy is comprised of personnel training (e.g., Trauma-informed care), integrated technology with a customized screening scoring and aligned service referral algorithm, team-based screening workflows, ongoing care team coaching, and peer support. Significant changes to the original study protocol were needed to accommodate the negative impact that the COVID-19 pandemic had in the partner FQHC system.

Hypotheses

1. ACEs screenings

- a. Clinics using implementation strategies will have higher rates of REACH of ACEs screenings compared to their screening rates before implementing the strategies.
- b. Clinics using implementation strategies will have higher rates of REACH of ACEs screenings than clinics screening for ACEs and as part of the state funded CALQIC project, without the implementation strategies.

- c. Exploratory: Are there any differences between in the effectiveness of the implementation strategies in different sub-groups (such as race, ethnicity, age and gender)?

2. Referrals to mental health services

- a. Clinics using implementation strategies will have higher rates of mental health referrals compared to their referral rates before implementing the strategies.
- b. Clinics using implementation strategies will have higher rates of mental health referrals than clinics screening for ACEs and as part of the state funded CALQIC project, without the implementation strategies.
- c. Among children screened, ACEs screenings indicating medium and high risk will lead to mental health referrals at higher rates than screenings indicating low risk.
- d. Exploratory: Are there any differences between in the effect of the implementation strategies on referrals in different sub-groups (such as race, ethnicity, age and gender)?

[figure not shown]
3. Implementation outcomes

- a. Perceive feasibility, acceptability, and usefulness of the intervention will be sufficiently high (see Table 1).

Study design:

Changes to the original study design were needed to accommodate the negative impact that the COVID-19 pandemic had in the partner FQHC system. We conducted a stepped-wedge design (SWD) trial with three sites, with data collection divided into 7 10-week intervals. Study sites remained in the intervention phase for multiple intervals to allow additional data to be collected. In addition to the 3 study sites, 2 additional sites from the same health system served as comparison sites, implementing ACEs screenings without the support of the implementation strategies. See Figure 1 for the SWD schedule.

Figure 1. Stepped-wedge schedule for the ACEs pilot study.

Study sites and patient eligibility:

The study statistician originally selected five clinics from a pool of 16 clinics providing family medicine, pediatric, or primary care for children ages 0 to 5 years old and across five regions to maximize variation (e.g., clinic characteristics such as resources and size). Clinics were located in urban, suburban, rural, and frontier communities. The study PI and FQHC champions invited the identified clinics via email to an informational video session to introduce the study and provided study informational materials to the clinic manager.

Once the pilot study started, two randomly selected clinics were not able to participate - one clinic closed and one clinic lost their pediatrician leading ACEs screenings. Due to extremely high staff turnover at the clinics and among FQHC leadership, additional clinics selected were not able to participate in this research study. Thus, from the three clinics that finished the stepped wedge schedule, one was randomly selected and two clinics joined based on their capacity to participate in a research study at that time.

Eligible children were those aged 0-5, on public insurance, attending a wellness visit with the participating clinician.

Data sources:

Data for the primary outcomes, including reach of ACEs screenings and mental health referral rates, was obtained via the electronic medical record (EMR) at the partner health system. Additional data for secondary analyses was collected using REDCap among intervention patients only, including the PSC scores and ACEs screening results. See Figures 2 and 3 for the Consort tables.

Figure 2. CONSORT table for the study pilot study – Electronic Medical Records Data.

[figure not shown]

Figure 3. CONSORT table for sub-sample of data – REDCap system.

[figure not shown]

Table 1. Description of measures

Measure	Description/psychometrics	Source
ACEs Screening		
PEARLS¹ screening (ages 0-11)	Caregiver-reported tool (17-items) designed to identify exposure to childhood adversity and stress factors that may lead to toxic stress and negative health outcomes. Number of endorsed events are summed up (0-4+) to identify risk level for toxic stress and potential symptomatology. English/Spanish	Caregiver
ACEs associated health conditions²	State-sponsored list with 25 ACEs associated health conditions for children ages 0 – 5. ² Physical conditions include asthma, allergies, unexplained somatic symptoms such as headaches. Mental health related conditions (over 10) include aggression, depression, ADHD, and anxiety	EMR system
Clinical screening tools	BPSC : 12-item screening measuring children's psychosocial functioning validated for children 0-18 months. Assesses irritability, inflexibility and difficulty with routines. ³ Designed for children 0-18 months; three subscales of four items each. Parents answer questions by selecting one of three responses: "not at all" = 0, "somewhat" = 1, "very much" = 2. Any summed score of 3+ on any of the three subscales indicates that a child is "at risk and needs further evaluation." Scores 0-2 indicates child "appears to meet expectations." Cronbach's alpha adequate for subscales (α =0.75 to 0.83). PPSC : 18-item screening for measurement of children's psychosocial functioning; validated for children ages 18-60 months. Assesses externalizing, internalizing, attention problems, and parenting challenges. ³ Parents select responses as: "not at all"=0; "somewhat"=1; "very much"=2. A score of 9+ indicates children is "at risk and needs further evaluation." α =0.92.	Caregiver
FIM⁴	Self-reported 4-item instrument to evaluate feasibility of implementation efforts. 4-pt Likert scale; average score of	Staff, manager

	4+ shows ACEs policy and implementation strategy perceived as feasible. Good internal consistency ($\alpha=0.89$). Test-retest reliability $r=0.88$.	provider
AIM⁴	Self-reported 4-item instrument to evaluate acceptability of ACEs policy and implementation efforts. 4-pt Likert scale; average score of 4+ shows acceptability. Good internal consistency ($\alpha=0.83$). Test-retest reliability $r=0.83$.	Staff manager provider
Fidelity	The implementation coach will use a checklist to observe the screening staff/providers at each clinic (once in week 5 of each 10-week trial period) to assess adherence to screening protocols and competence of performance. She will identify deviations/concerns and provide immediate feedback. We expect at least 67% fidelity (number of endorsed deviations / all items in the checklist) based on a previous study ⁵ The coach will also document adaptations and emerging challenges and report back to the PI and TIC workgroup. Form will be developed by PI & [name]. Observation checklists/ audits are effective strategies to improve fidelity of performance. ⁶	Implem coach
Reach	Measured as a proportion = number of eligible visits in a 10-week period divided by the number of PEARLS and clinical (BPSC/PPSC) screenings. Expect between 80%-92% of eligible children will be screened as threshold; based on pediatric screening studies in primary care. ^{7,8}	EMR system
Mental health referrals	Number of mental health referrals (behavioral analysis, behavioral health, care coordinator, care management, child development/development center or social work) divided by the total # of eligible children in a 10-week trial period. expect 11.4% increased referral rate based on a similar study ⁹ and using current referral rate of 3.8% to inform this threshold [per i2itracks report	EMR system
Changes in BPSC/PPSC	Mean score differences from eligible child visits in each 10-week period. Compare those means in pre vs post implementation periods. No threshold as we will test a two-tail hypothesis for this measure given mixed evidence on the impact of screening policies on access to care and clinical outcomes. ^{10,11} Even if a positive effect is not found, this information is still valuable for implementation and leadership.	EMR system

Measures		
Implementation leadership (ILS)¹²	12-item scale with four subscales measuring proactive leadership, knowledgeable leadership, supportive leadership, and perseverant leadership. Reliability for the total scale is strong ($\alpha=0.98$). An average score of 4+ used as threshold; 5-point Likert scale (not at all-very great extent). Subscale score is based on the mean score for the items; total score is the mean of the subscale scores ¹² ;	Staff provider
Implementation climate¹³	6-item scale measuring the strategic climate for the implementation of interventions. The average interrater agreement: $r^*wg (J) = 0.76$ for the group referenced scale. Items are rated on a 5-item Likert scale (completely disagree-completely agree). Average score of 4+ as threshold ¹³	Staff provider
Covariates		
Child characteristic	Variables include sex, self-identified race and ethnicity, age, language of preference for health care receipt, born in the USA. Note: EMR system does not report data on caregivers of child patients	EMR system

Statistical analysis:

Descriptive statistics will be used to describe the sample of children and clinics. The sample will be described using counts and percentages, and treatment groups will be compared using chi-squared tests. We will calculate risk differences with confidence limits for each of our three groups of interest- the study clinics during the control period, study clinics during the intervention period, and the control clinics. For subgroup analyses exploring differences by child demographics, we will calculate risk differences within those subgroups (age, gender, race, and ethnicity).

The reach variable (proportions screened) will be analyzed using binary regression (a generalized linear model, specifying a binomially-distributed dependent variable and identity link function). Modified Poisson regression with robust variance estimation¹⁴ will be used to analyze mental health referrals to estimate adjusted risk differences. Both models will compare the intervention and control arms as the primary independent variable of interest. Possible covariates will include child's sex, age category (<18 months, 18-60 months), child's race (white, black, other/unknown), child's ethnicity (Latino, not Latino, unknown/not reported), language of preference, and study site; covariates will be included in their adjustment changes the intervention regression coefficient by more than 15%.

Models comparing the intervention and comparison clinics will be adjusted for the child's race and for the study site. Missingness in demographic data will be handled by including an 'unknown or not reported' category. Survey data will be analyzed using aggregated intra-class correlations (ICC) to assess within-group agreement, whether clinic care teams shared perceptions of readiness for change during the preparation phase, and implementation climate and leadership. ICC is the variance proportion attributed to care teams.¹⁵ Higher scores in these measures reflect higher organizational support for the translation of a new clinical practice into practice.¹⁶ An agreement of 0.70 or higher reflects an organizational measure.¹⁷

References

1. National Pediatric Practice Community. PEARLS FAQs. Accessed August 14, 2019. <https://nppcaces.org/faqs/>
2. Aware A. ACES Screening Clinical Workflows. Accessed June 15, 2020. <https://www.acesaware.org/wp-content/uploads/2019/12/ACE-Clinical-Workflows-Algorithms-and-ACE-Associated-Health-Conditions.pdf>

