Inclusion criteria. Clinic eligibility is defined by: provision of pediatric care (i.e., family medicine, pediatric, primary care) for child patients ages 0-5 years old. Caregiver eligibility for reporting of the PEARLS and Pediatric Symptoms Checklist (PSC) on their child's behalf and interviews: Adults ages 18 years and older with legal custody or with the authority to arrange care for the child. Clinic staff eligibility for interviews: Clinic personnel involved directly or indirectly in the planning and/or implementation of the ACEs Aware policy.

Exclusion criteria. Clinics not providing pediatric care (i.e., family medicine, pediatric, primary care) for child patients ages 0-5 years old. Caregivers that are not a legal guardian or someone with written authorization at the clinic to make decisions for the child. Clinic staff being a new hire and/or not having

participated directly or indirectly in the implementation of the ACEs Aware screening at their clinic.

b. Rationale for excluding children: We are not recruiting children for data collection during screenings at the clinic visit because their caregiver will report on their behalf based on two screenings (PEARLS and PSC). Child data on referrals to mental health services and socio-demographic characteristics will be obtained directly from the child's clinical chart (EMR system) and after obtaining signed consent and HIPAA authorization forms from each caregiver. *The ACEs screenings are happening at the clinics regardless of this study.*

c. Participants are part of two groups of special populations:

- 1) Clinic Employees: For Aim 2, we will invite clinic personnel to be part of interviews to evaluate the success of our implementation strategies based on their experiences. That means, we will survey them and ask follow-up interview questions assessing their acceptability, feasibility and lessons learned from their experience with the screening process at the clinic.

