- 2) Non-English-Speaking Caregivers: For Aim 2, we will randomly select caregivers at each clinic whose children were screened for ACEs to participate in phone interviews about their perceptions of the screening process. We will also gather basic caregiver sociodemographic information (age, gender, education). Spanish-speaking caregivers will be interviewed by a fluent Spanish speaker (e.g., The PI is Latinx scholar and Spanish is her first language). For the child screenings (Aim 1), we will follow the clinics' procedure. That is, when the caregiver makes an appointment for their child, they are asked if they would like a translator. Every clinic has someone who speaks Spanish and two have someone who speaks Arabic. In the event that there would not be a Spanish-speaking staff member available, translation services are available.

IV. Recruitment/Screening Process (sampling strategy)

- a. Recruitment will take place at five Federally Qualified Health Center (FQHC) clinics located in under-resourced communities in California. We do not have exact locations yet because these five clinics will be randomly selected from a total of 28 clinics located in multiple counties (e.g., Riverside, San Bernardino, San Diego).
- b. Recruitment of caregivers for participation in the ACEs screenings and to allow access to their child's EMR data: Once the caregiver checks-in at the front desk, the medical assistant (MA) individual will meet the family and will walk them to the examination room for their wellness visit (part of routine care procedure). As part of this event, the MA will introduce the study and obtain consent from the caregiver for participation. Here, caregivers can decline, in which case the MA will continue with the wellness visit procedure that includes screening for ACEs using the PEARLS tool (this screening is happening at the clinics and regardless of this study). The FQHC's data analyst will receive the list of children who had been screened and consented to be in the study and will provide EMR data to the PI based on the study design schedule. Note: If the caregiver declines to participate in this study, the screener will not use the REDCap programmed tablets as we will not have that caregiver's screening data at all.

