 - 4.6 Month 4: The PI and consultant ([name]) will pre-record 3 video-training sessions on study procedures and protocols, caregiver consent process and administration of the PSC survey (in 2020, all clinic personnel at the FQHC partner have already completed a 2-hour online training on how to administer the PEARLS screener)

- 4.7 Month 5: Screeners at each selected clinic will go over the videos for training. The PI and [name] will schedule a follow up 45-min call with each screener to discuss videos and learning/questions.
- 4.8 Months 6 – 7.5: Baseline starts in all five selected clinics. Pre-intervention data will be collected from the clinics over a 10-week period. Clinic staff will be told to follow the ACEs state requirements, which include the PEARLS screenings, ACEs-related health conditions checklist, wellness exam, follow-up education, and mental-health referrals if deemed appropriate. Mediators data will be collected at the end of this period.
- 4.9 Months 7.5 to 30 / Trial starts:
 - 4.9.1 During a 10-week trial period for each clinic (data collection will continue until the end of the trial), each clinic switching from control to intervention status will start using the implementation strategies (i.e., support from the trained implementation coach, TIC workgroup guidance/advise, use of electronic tablets for screenings and service referrals).
 - 4.9.2 Due to the human and financial impact of COVID-19 epidemic, the randomized control clinics had not implemented ACEs screening at the time of the pilot starting. We have identified two clinics within the healthcare system, not part of the trial, that have started implementing ACEs screening. These two clinics will serve as non-randomized comparison groups for this study. We will compare our study clinics and these comparison clinics on ACEs screenings and on referrals to mental health services.
 - 4.9.3 Steps for ACEs screenings with caregivers:
 - 4.9.3.a. When a child and their caregiver come to the clinic for the wellness visit, screening staff will conduct the study screenings using a tablet device that has the REDCap database on it. This should take 10 minutes.

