Quantitative data: We will use descriptive statistics (i.e., frequencies, means and standard deviation estimates) to describe the analytical sample. We will examine whether the implementation strategies (i.e., advisory board, use of REDCap handheld tablets, use of the PSC tool and an implementation coach) increases the number of children screened and referred to support services, compared to baseline. To do that, we will use methodology that accounts for repeated measures over time and that accounts for both within-person and across-person variation (i.e., Generalized linear mixed model (GLMM)) while controlling for clustering of patients within clinics and possible confounding by calendar time. *Our analysis will include sex as a biological variable, testing for a differential effect on outcomes by child sex.* We will report the magnitude of missing data and compare demographic and clinic characteristics and outcomes between observations with versus without missing data. In sensitivity analyses, we will perform multiple calculations (i.e., imputations) using fully conditional specification to obtain 10 complete datasets; summary estimates of intervention effects with 95% confidence limits over the 10 datasets will incorporate within- and between-dataset sampling variability.

Comparison of randomized intervention sites to non-randomized control sites

Due to the human and financial impact of COVID-19 epidemic, the randomized control periods had not implemented ACEs screening at the time of the pilot starting. We have identified two clinics that have implemented ACEs screening that are not part of the trial.

To obtain an additional non-randomized estimate of the intervention effect, we will compare:

- (1) the control periods in the randomized clinics to comparable time periods in the non-randomized clinics;
- (2) the intervention periods in the randomized clinics to comparable time periods in the non-randomized clinics.

We will use the same GLMM models as described above, with indicator variables for non-randomized vs randomized clinic, and randomized control vs intervention periods. Groups will be compared on ACEs screenings, and mental health referral rates.

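### If control-period reach is at or near zero, as the protocol suggests, H1a sets almost no bar and its identity-link model sits on its boundary

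*SAP*

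**What the plan says.** **The hypothesis.** SAP, Hypotheses, 1a: "Clinics using implementation strategies will have higher rates of REACH of ACEs screenings compared to their screening rates before implementing the strategies". No minimum difference is attached. Only 1c and 2d are marked exploratory. SAP, Data sources, lists reach among the primary outcomes.

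**The control condition.** The protocol gives two accounts.

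- Not screening: step 4.9.2 says "the randomized control clinics had not implemented ACEs screening at the time of the pilot starting", and section V.c, on the comparison with non-randomized sites, says "the randomized control periods had not implemented ACEs screening at the time of the pilot starting". Both attribute this to COVID-19.
- Screening ongoing or planned: section III.b says "The ACEs screenings are happening at the clinics regardless of this study", section IV.b says "this screening is happening at the clinics and regardless of this study", and step 4.8, on the baseline period, says "Clinic staff will be told to follow the ACEs state requirements, which include the PEARLS screenings".

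SAP, Study sites and patient eligibility, adds that only one of the three clinics that completed the schedule was randomly selected. The other two joined because they had capacity. Their baseline screening is not described, and the SAP does not mention a no-screening baseline.

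**The yardstick.** SAP Table 1, Reach: "Expect between 80%-92% of eligible children will be screened as threshold". This is not made a criterion for H1a.

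**The model.** SAP, Statistical analysis, uses binary regression for reach, "specifying a binomially-distributed dependent variable and identity link function". Study site is one of several possible covariates, kept if it shifts the intervention coefficient by more than 15%. No calendar-time term is named. The protocol's mixed model (V.c) does account for clinic clustering and calendar time.

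**The concern.** The intended contrast was policy plus strategies against policy alone. If the clinics were not screening in their control periods, H1a compares having started with not having started. A significant result could then be reported as effectiveness of the strategies when it mainly records that screening began, whether because of the strategies or because clinics were recovering from the pandemic. Nothing in H1a requires reach to come near the level the SAP expects.

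The definition of reach can push the same way. Table 1 counts PEARLS and BPSC/PPSC screenings together. The PSC is Activity 3 of the strategy, and SAP, Data sources, says the REDCap data that include PSC scores came from intervention patients only. If both screens are needed to count, control reach would be near zero even where PEARLS was in use.

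A zero control count also puts the planned regression at the edge of its parameter space, where its adjusted estimate and Wald interval cannot be trusted.

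**Working it through.** The documents give no sample size, power or alpha for H1a, so there is no stated figure to reproduce. What follows is illustrative. Assumptions: two-sided 0.05, children independent, group sizes chosen to span a plausible range. The only child count in the protocol is 450 (records kept in REDCap); 225 is half of it.

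**1. How many screened children make H1a significant against none?** With 0 of n0 in control and k of n1 in intervention, the probability that all k fall in the intervention group is C(n1,k)/C(n0+n1,k). For equal groups the two-sided Fisher p is twice this. For n=100 and k=6: 2 × (100·99·98·97·96·95)/(200·199·198·197·196·195) = 0.029. For k=5 it is 0.059. For unequal groups, p sums all tables no more probable than the one observed.

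| Control | Intervention | Smallest k | Reach | p |
|---|---|---|---|---|
| 0/100 | 100 | 6 | 6.0% | 0.029 |
| 0/200 | 200 | 6 | 3.0% | 0.030 |
| 0/225 | 225 | 6 | 2.7% | 0.030 |
| 0/400 | 400 | 6 | 1.5% | 0.031 |
| 0/200 | 400 | 9 | 2.25% | 0.033 |
| 0/150 | 450 | 12 | 2.7% | 0.044 |

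**2. How likely is that?** With 225 per condition and a true intervention reach of only 5%, P(X ≥ 6) for X ~ Binomial(225, 0.05) is 0.97. At 10% it is about 1.00.

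**3. Does it need an exact zero?** No. With 225 per condition, the smallest significant intervention reach is 10.2% if control reach is about 5%, 28.4% if 20% and 87.6% if 80%. The bar becomes demanding only when control reach is substantial.

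**4. What does the identity-link model do with zero control events?** Take one binary covariate X, split evenly in each arm: reach = a + dT + bX, where T marks intervention, r0 and r1 are intervention reach at X=0 and X=1 (r1 > r0), and p is their mean. The maximum lies at a = 0. At b = 0 and d = p, the likelihood slope in b is (n1/2)(r1 − p)/[p(1 − p)] − n0/2. If this is zero or negative, b is held at 0. If positive, b rises and the model assigns reach b to control children with X=1, none of whom was screened.

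| n0 / n1 | r0, r1 | First term vs n0/2 | b | Adjusted RD | Crude RD |
|---|---|---|---|---|---|
| 200/400 | 50%, 70% | 83.3 < 100 | 0 | 0.600 | 0.600 |
| 100/400 | 50%, 70% | 83.3 > 50 | 0.072 | 0.566 | 0.600 |
| 200/400 | 40%, 90% | 219.8 > 100 | 0.233 | 0.560 | 0.650 |
| 80/450 | 40%, 80% | 187.5 > 40 | 0.291 | 0.462 | 0.600 |

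X is balanced, so it does not confound and adjustment should leave the risk difference alone. In the first row a true 20-point covariate effect is erased. In the last, the risk difference moves by (0.600 − 0.462)/0.600 = 23%, which exceeds the SAP's 15% rule and would bring X into the model.

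**5. Standard errors.** The control arm's Wald variance, p(1 − p)/n, is 0 at p = 0; a simulated fit with 0/200 in control returned about 2e-9. In the first row the standard error of the risk difference is √(0.6 × 0.4/400) = 0.0245, all of it from the intervention arm. The exact 95% upper limit for 0/200 is 1 − 0.025^(1/200) = 1.8%, so the control rate is not known without error.

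**The case against.** The strongest reply is that the investigators saw the problem and dealt with it. The protocol discloses the missing screening and adds two clinics that do screen. The SAP tests against them in H1b and gives an expected reach. It also reports risk differences with confidence limits, so 6% reach would appear as about 6 points and not as a bare success. Fisher's test is not the method named for reach, and the figure of 6 children needs equal groups. All of this stands. It limits the harm but leaves H1a as a directional hypothesis on a primary outcome that a trivial rise would satisfy.

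A second reply is that the system adopted the policy in August 2020. If clinics under that policy were not screening, zero is the policy-alone result, and getting screening started is part of what an implementation strategy is for. This stands in part: a rise to 80% or more would be informative. Attribution remains open because the protocol blames COVID-19 for the absence, the comparison clinics screened without the strategies, and the SAP reach model has no calendar-time term.

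A reader might infer that H1a is a failed primary hypothesis tested against a structural zero and can show nothing about the strategies. The documents do not support that. No hypothesis is labelled primary. The no-screening statements concern randomized clinics or periods at pilot start, conflict with III.b, IV.b and step 4.8, and do not settle the baseline of the two other clinics. Nor does a zero control count always force covariate effects to 0: three of the four cases above show otherwise. The standard error of the risk difference also remains of ordinary size even where the control-arm one collapses.

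**Conclusion.** The point holds conditionally. If control-period reach is zero or close to it, H1a can be met at reach of roughly 1.5% to 6% in the group sizes shown, against an expected 80%-92%. It then cannot by itself distinguish the strategies from the start of screening. At exactly zero control events, the planned covariate-adjusted identity-link analysis is unreliable: it suppresses real covariate effects or lets a balanced covariate move the risk difference, by as much as 0.14 in the cases tried.

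This rests on the protocol's statements about pilot start applying to the control data actually analysed, which the documents leave unclear. The thresholds assume two-sided 0.05 and independent children; the group sizes and covariate patterns are illustrative.

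**What to change.** 1. Reconcile protocol sections III.b, IV.b, steps 4.8 and 4.9.2, and V.c on whether screening took place in control periods. Report control-period PEARLS counts and eligible visits by clinic and 10-week interval.
2. Present H1a as an estimate of reach once screening was introduced with the strategies, not as a test of effectiveness over unsupported screening. State that the SAP model does not separate it from calendar time.
3. Compare intervention-period reach with the 80% threshold in Table 1, clinic by clinic, with confidence intervals.
4. Where control counts are zero, use an unadjusted score or exact interval for the risk difference in place of the covariate-adjusted identity-link Wald interval.
5. Rest any claim of benefit over clinics already screening on H1b, stating that it is non-randomized, three clinics against two. Do not re-designate it as the primary hypothesis: the SAP describes the trial in the past tense, so that would be a change made after the data.

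The cost is some SAP wording, one table of counts and a few lines of code. The downside is a more modest headline claim. Giving up adjustment where control counts are zero loses little, since the adjusted figure is not dependable there.
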